8.9.5 Physical Exams

Physical exam finds will be recorded by the sites within medical history or adverse events and are otherwise not summarized.

8.10 Population Pharmacokinetics Analysis

The plasma concentrations of serlopitant and metabolites will be combined with the data from other serlopitant clinical studies for population PK analysis with PK endpoint of individual model parameter estimates and covariates identification. A specific population PK data analysis plan will be developed that will outline the detailed approach to data handling, model development and diagnostics, individual model parameter estimation, exploration of covariate effects, and final model evaluation techniques. The population PK analysis report will not be a part of the clinical study report for MTI-117.

9 ADMINISTRATIVE ASPECTS

9.1 Changes to the Protocol

Protocol amendments must be made only with the prior written approval of the Sponsor. An investigator signature will be obtained for the initial protocol and any amendments. Substantial amendments will be provided to the appropriate regulatory authorities. No protocol changes affecting the following will be made without the written approval of the Sponsor and the responsible IRB or EC:

- Safety and/or eligibility of subjects
- Data integrity
- Study design or conduct
- Willingness of a subject to participate in the study

9.2 Study Termination

The Sponsor has the right to terminate this study at any time. Reasons may include, but are not limited to, evidence of a potential safety risk in this study or other serlopitant studies or poor enrollment. The study may be terminated at the request of the US Food and Drug Administration, or if the approval to manufacture or to import study drug is revoked by those with jurisdiction. A written statement fully documenting the reasons for study termination will be provided to the IRB or EC.

9.3 Monitoring and Auditing Procedures

The Sponsor will designate study monitors who will be responsible for monitoring the conduct of this study. A separate study Monitoring Plan will include details regarding the responsibilities of the study monitors, investigator responsibilities in providing access to records and addressing issues identified, the frequency and structure of monitoring visits, and adherence to subject confidentiality as outlined in the Informed Consent Form (ICF).

9.4 Transfer of Obligations

The Sponsor may delegate certain aspects of study oversight to Contract Research Organizations (CROs). The specific responsibilities will be detailed in Transfer of Obligations documents.

9.5 Informed Consent

The purpose of the study, the procedures to be carried out, and any potential risks of study participation will be described in non-technical terms in the ICF. After having reviewed and understood the ICF, subjects will be required to read, sign, and date an IRB-approved or EC-approved consent form before any study-specific procedures are carried out. Subjects will be assured that they may withdraw from the study at any time without jeopardizing medical care related to or required as a result of study participation. The original signed consent form will be maintained in the investigator site file. Copies of signed consent forms will be provided to the subject.

9.6 Communication with the Institutional Review Board or Ethics Committee

The IRB or EC is constituted and operates in accordance with the principles and requirements described in the ICH E6 guideline. The protocol, ICF, other written subject information, and any proposed study advertising material must be submitted to the IRB or EC for written approval. IRB or EC approval of these documents will be provided to the investigator. The study will not start until the IRB or EC has granted its approval of the study materials and procedures.

Protocol amendments will be submitted to the IRB or EC as explained in [Section 9.1](#). SAE information will be submitted to the IRB or EC as explained in [Section 7.4](#).

If the study is terminated by the Sponsor, a written statement fully documenting the reason(s) for study termination will be provided to the IRB or EC.

9.7 Disclosure and Confidentiality

By signing this protocol, the investigator agrees to keep all information provided by the Sponsor in strict confidence and to require the same confidentiality from site staff and the IRB or EC. Study documents provided by the Sponsor (e.g. protocol, IB, eCRFs) will be stored appropriately to ensure their confidentiality. The information provided by the Sponsor to the investigator may not be disclosed to others without direct written authorization from the Sponsor, except to the extent necessary to obtain informed consent from subjects who wish to participate in the study.

The investigator must ensure that the subjects be identified by a unique subject study number. Other study-related documents that may contain confidential participant information (e.g. signed ICFs) will be kept in strict confidence by the investigator and be stored in a secure location with access restricted to the study staff.

9.8 Records and Electronic Case Report Forms

All study data except central laboratory, PK, IWRS, eDiary, and ECG data will be recorded in an eCRF system (note: collection of central laboratory and PK blood draws will be recorded in the eCRF). Data will be entered at the site by the appropriately designated and trained site personnel. All source documents from which eCRF entries are derived should be placed in the subject's medical records. eCRFs will be completed for every subject screened in the study.

The study monitor will review all eCRFs in detail and will have access to participant medical records, laboratory data, and other source documentation to allow required eCRF fields to be verified by source data.

Data consistency and plausibility checks against data entered into the eCRF will be included in the eCRF system. Data corrections can be performed in the eCRFs by the site. For each instance of data modification, the system requires a reason for change. The system keeps a full audit trail of the data values, the date and time of modification, and the electronic signature of the user who performed the change.

After a full review of the eCRFs by the study monitor and resolution of any data clarifications, the investigator will review, sign, and approve the subject's eCRF. All essential documents, source data, clinical records, and laboratory data will be retained by the site in accordance with the ICH E6 guideline and the site's data retention policies. These records must be available for inspection by the Sponsor, monitor, and regulatory authorities.

Further detail regarding data management and eCRFs is included in the Data Management Plan.

9.9 Good Clinical Practices and Ethical Study Conduct

The study procedures outlined in this protocol will be conducted in accordance with applicable ICH Guidelines, including ICH E6: Good Clinical Practices. As this study is conducted under a US IND, the investigator will also ensure that the basic principles of "Good Clinical Practice", as outlined in 21 CFR 312, subpart D, "Responsibilities of Sponsors and Investigators", 21 CFR, part 50 and 21 CFR, part 56 are adhered to.

The study procedures outlined in this protocol will also be conducted in accordance with the principles of the Declaration of Helsinki.

9.10 End of Study Notification

The Sponsor will notify appropriate regulatory authorities and the IRB or EC within 90 days from the end of the clinical study. The end of the clinical study is defined as the last study visit for the last subject.

9.11 Publication of Results

All publications (e.g. manuscripts, abstracts, oral/slide presentations, book chapters) based on this study or relying on data from this study must be submitted to the Sponsor for review and release before submission for publication. The Sponsor is responsible for final approval of all publications.

9.12 Final Report

A clinical trial summary report will be provided to the appropriate regulatory authorities within one year of the end of the clinical study.

APPENDIX A SCHEDULE OF ACTIVITIES AND ASSESSMENTS

Table 2 Schedule of Visit Activities

Examination	Screening	Mid-Screening ^{TC} (-3 days)	Baseline ¹ (+3 days)	Week 1 ^{TC} (± 3 days)	Week 2 (-3 /+1 days)	Week 4 (± 3 days)	Week 6 (± 3 days)	Week 8 ^{TC} (± 3 days)	Week 10 (+ 3 days)	F/U ²
Demographics	X									
Informed consent	X									
Paper WI-NRS ³	X									
WI-VAS			X		X	X	X		X	X
ESS			X		X	X	X		X	X
sPGA			X		X	X	X		X	X
PGIC					X	X	X		X	X
ECG	X					X				X
Vital signs	X		X		X	X	X		X	X
Medical history (and prior medications)	X	X	X							
Physical exam ⁴	X		X			X	X		X	X
Concomitant medications			X	X	X	X	X	X	X	X
Labs ⁵	X					X			X	X
Urine pregnancy test ⁶	X		X			X			X	X
PK blood draw									X	
Review of I/E criteria	X	X	X							
Dispense/collect eDiary	X									X
eDiary review/compliance ⁷		X	X	X	X	X	X	X	X	X
Dispense and/or collect study drug			X		X	X	X		X	
Review study drug compliance				X	X	X	X	X	X	
AEs/SAEs ⁸	X	X	X	X	X	X	X	X	X	X

^{TC}Telephone Contact: The Mid-Screening telephone contact should occur at least 15 days prior to the scheduled Baseline visit.

¹All visits and windows should be scheduled based on the Baseline Visit (Day 1)

²The Follow-up (F/U) visit occurs 35 days (+ 7 days) after the Week 10 visit or the last dose of study drug for subjects who discontinue study drug early.

³WI-NRS at Screening visit will be collected manually on paper for Inclusion/Exclusion criteria. All subsequent WI-NRS are collected daily via eDiary.

⁴Screening physical exam is complete and includes height and weight; other physical exams are targeted and include weight.

⁵Labs are ideally performed in the morning, particularly at visits with endocrine assessments (including Reproductive Endocrinology for females under 55 at age of consent who are not using hormonal contraception or other hormonal therapies at Screening) at Screening, Week 10, and Follow Up).

⁶Female subjects of childbearing potential only. Serum pregnancy test is required for positive or equivocal results.

⁷See Table 3 for eDiary assessments

⁸During the period between informed consent and first study drug dose, only SAEs caused by a protocol-mandated intervention will be collected.

Table 3 Schedule of eDiary Assessments

An eDiary device is provided to subjects at the Screening visit and collected at the Follow-up visit.

Device	Assessment	Frequency and Duration of Assessment
eDiary	WI-NRS	Once daily from Screening visit through the Follow-up visit
eDiary	Dosing	Once daily from Baseline visit through Week 10 visit or study drug discontinuation

APPENDIX B LIST OF STRONG CYP3A4 INHIBITORS

The list of strong CYP3A4 inhibitors is based on the FDA list effective September 26, 2016, *Examples of clinical inhibitors for P450-mediated metabolisms (for concomitant use clinical DDI studies and/or drug labeling* ([“Examples of clinical inhibitors for P450-mediated metabolisms \(for concomitant use clinical DDI studies and/or drug labeling \(9/26/2016\)”](#))).

Note: This Appendix may be replaced if applicable (e.g., if updated by the FDA) through site communications without requiring a protocol amendment.

1. boceprevir
2. clarithromycin
3. cobicistat
4. conivaptan
5. danoprevir and ritonavir
6. diltiazem
7. elvitegravir and ritonavir
8. idelalisib
9. indinavir and ritonavir
10. itraconazole^a
11. ketoconazole^a
12. lopinavir and ritonavir
13. nefazodone
14. nelfinavir
15. paritaprevir and ritonavir and (ombitasvir and/or dasabuvir)
16. posaconazole^a
17. ritonavir
18. saquinavir and ritonavir
19. telaprevir
20. tipranavir and ritonavir
21. troleandomycin
22. voriconazole^a
23. regular grapefruit juice consumption (note: The effect of grapefruit juice varies widely among brands and is concentration-, dose-, and preparation-dependent. Grapefruit juice may be a strong or a moderate CYP3A inhibitor depending on the preparation)^b

^a When administered topically, it may not be considered a strong CYP3A4 inhibitor due to limited systemic absorption.

^b The occasional consumption of grapefruit juice or the consumption of grapefruit or other citrus fruits (e.g., pomelo, lemon, lime, Seville orange, bitter orange, starfruit) is not contraindicated.

[figure not shown]
APPENDIX C WORST ITCH NUMERIC RATING SCALE QUESTIONNAIRE

NRS for Itch Intensity

For the following item, please provide the response that best describes your itching on the Numeric Rating Scale where 0 = No itch and 10 = Worst itch imaginable

CIRCLE THE NUMBER ON THE SCALE THAT CORRESPONDS WITH YOUR INTENSITY LEVEL

How would you rate your **WORST** itch in the past 24 hours, on a scale from 0 to 10, where 0 is No itch and 10 is Worst itch imaginable?

APPENDIX D EPWORTH SLEEPINESS SCALE

How likely are you to doze off or fall asleep in the following situations, in contrast to just feeling tired?

This refers to your usual way of life recently.

Even if you haven't done some of these things recently, try to figure out how they would have affected you.

Use the following scale to choose the **most appropriate number** for each situation:

- 0 = **no chance** of dozing
- 1 = **slight chance** of dozing
- 2 = **moderate chance** of dozing
- 3 = **high chance** of dozing

It is important that you answer each item as best as you can.

Situation	Chance of Dozing (0-3)
Sitting and reading _____	_____
Watching TV _____	_____
Sitting inactive in a public place (e.g., a theater or a meeting) _____	_____
As a passenger in a car for an hour without a break _____	_____
Lying down to rest in the afternoon when circumstances permit _____	_____
Sitting and talking to someone _____	_____
Sitting quietly after a lunch without alcohol _____	_____
In a car or bus, while stopped for a few minutes in traffic _____	_____

THANK YOU FOR YOUR COOPERATION

ESS © MW Johns 1990-1997. Used under License

1 STUDY DESCRIPTION

1.1 Introduction

In this study, serlopitant is being studied for the treatment of pruritus (itching) in adults with chronic pruritus of unknown origin. Pruritus, or itch, is defined as an unpleasant sensation that elicits the desire or reflex to scratch (Ikoma 2006). Chronic pruritus may be associated with a variety of underlying conditions, including both dermatological and systemic diseases. However, in 8-15% of patients with chronic pruritus, an underlying etiology cannot be identified (Weisshaar 2012).

Serlopitant is a small molecule, highly selective neurokinin-1 receptor (NK₁-R) antagonist that is administered orally. NK₁-R stimulation has been shown to be an important pathway for pruritus perception (Ständer 2015). Evidence suggests that inhibition of this pathway results in decreased pruritus, see protocol for details. Prior to initiation of this study, serlopitant was evaluated in over 1,500 subjects.

1.2 Objectives

Study MTI-117 contains primary and secondary objectives.

- The primary objective of this study is to assess the efficacy of repeated oral doses of serlopitant in adult subjects with chronic pruritus of unknown origin.
- The secondary objective of this study is to assess the safety and tolerability of repeated oral doses of serlopitant in adult subjects with chronic pruritus of unknown origin.

1.3 Study Design

This is a double-blind, randomized, placebo-controlled study. Subjects will be randomized in a 1:1 ratio to receive daily oral doses of serlopitant 5 mg or placebo for 10 weeks. After completion of the treatment period or early discontinuation of study drug treatment, all subjects will enter a 5-week follow-up period.

The study will consist of three periods, for a total study period of 18 weeks:

- Screening period: 3 weeks
- Treatment period: 10 weeks
- Follow-up period: 5 weeks

Informed consent may occur prior to the Screening visit. During the screening period, subjects will be assessed for conditions associated with chronic pruritus. If the investigator deems that additional assessments are necessary to rule out specific conditions the subject may not be randomized until these are completed and the pruritus is still considered to be of unknown origin.

Subjects will be provided an electronic diary (eDiary) at the Screening visit and are to complete the diary daily until the end of study participation. See [Section 2.3.1](#) for more detail. At the Baseline visit (Day 1), subjects will take a loading dose (3 tablets taken orally) at the site. Starting on Day 2, subjects will take one tablet per day until Week 10 or until the study drug is discontinued.

The primary efficacy endpoint is the Worst-Itch Numeric Rating Scale (WI-NRS) 4-point responder rate at Week 10. This endpoint is based upon the WI-NRS results entered into the eDiary. Other efficacy endpoints are captured within the case report forms. Safety endpoints are captured within the case report form or central laboratories.

An abbreviated schedule of activities for the study can be found in [Table 1](#), with greater details of the schedule available in the protocol.

Table 1 Schedule of Visit Activities

Examination	Screening	Baseline	Week 2	Week 4	Week 6	Week 10	F/U
Demographics	X						
Paper WI-NRS	X						
Daily WI-NRS	X						
WI-VAS / ESS / sPGA		X	X	X	X	X	X
PGIC			X	X	X	X	X
ECG	X			X			X
Vital signs	X	X	X	X	X	X	X
Medical history / prior and current medications	X	X					
Physical exam	X	X		X	X	X	X
Concomitant medications / emollients		X	X	X	X	X	X
Hematology/Chemistry	X			X		X	X
Endocrine/Reproductive	X					X	X
Serology, Serum IgE, Iron, Other labs	X						
Urine pregnancy test	X	X		X		X	X
PK blood draw						X	
Dispense / collect study drug		X	X	X	X	X	
AEs/SAEs	X						

1.4 Method of Assigning Subjects to Treatment Groups

Subjects will be randomized to serlopitant 5 mg or placebo in a 1:1 ratio. Stratified permuted block randomization will be used. Randomization will be stratified by the subject's reported WI-NRS score for the 1-week period prior to the Baseline visit (7 to < 8.5, 8.5 to 10), and by the subject's age at the Baseline visit (18 to < 50 years, ≥ 50 years). Randomization of subjects < 50 years of age will be capped at 25% of the total randomized population. This cap may be increased up to 33% of the total randomized population at the Sponsor's discretion. An Interactive Web Response System will be used to perform the randomization.

1.5 Treatment Blinding

This is a double-blind study. Unless required for safety reporting, the sponsor will not have access to unblinded data during the study and there is no expectation that the study data (e.g. adverse events, dosing, or lab results) will unblind the sponsor, investigator or subjects. The investigator can unblind individual subjects for emergency medical purposes. Greater details concerning study blinding can be found in a separate blinding plan.

1.6 Decision Rule and Sample Size

The significance level for this study is 5% (one-sided). If the one-sided p-value is less than 5% then the null hypothesis of no treatment effect is rejected. If the one-sided p-value is additionally less than 2.5%, then the serlopitant-based regimen will have met the generally accepted level of evidence required to demonstrate efficacy.

The target sample size of 200 randomized and dosed subjects (100 per group) has been determined based upon a 1:1 allocation of subjects to treatment groups and a 5% one-sided alpha level. A sample size of 200 subjects results in at least 90% power assuming a placebo 4-point responder rate of ███% and serlopitant 4-point responder rate of ███% at Week 10.

The sample size calculations have been performed in PASS 13 (“PASS 13 Power Analysis and Sample Size Software” 2014) and used a Chi-Squared test. The primary analysis will control for the stratification factors. It is expected that this unstratified power estimate will under-estimate the true power as it does not take the variance reduction resulting from stratification into account ([Matts and Lachin 1988](#)).

2 STATISTICAL METHODS

2.1 Populations Analyzed

Five analysis populations will be defined. These populations are:

- Screened Population – All subjects who provide informed consent.
- Randomized Population – All subjects who are randomized. Subjects will be analyzed within the treatment group to which they are randomized.
- Screen Failures – All screened subjects who are not randomized.
- Full Analysis Population (FAP) – Subset of subjects in the randomized population who were dispensed study medication. Subjects will be analyzed within the treatment group to which they are randomized.
- Safety Population – Subset of subjects who received at least one dose of study medication. This population will be analyzed based upon the actual treatment received. If a dosing error occurs and the subjects received both placebo and serlopitant they will be summarized in the serlopitant treatment group.

2.2 Study Drug Dosing and Compliance

Study drug accountability (i.e. how many tablets were dispensed and returned, date of first and last dose) will be recorded in the case report form. Additionally, subjects will record daily dosing within the eDiary. The tablet counts reported within the CRF will be used as the dosing and compliance data source. From these data the duration of treatment, number of tablets used, and compliance with treatment will be determined. The duration of treatment is

$$\textit{last dose date} - \textit{first dose date} + 1.$$

Compliance will be calculated as,

$$\textit{Compliance}(\%) = \frac{\textit{Tablets Used}}{\textit{Treatment End date} - \textit{Treatment Start date} + 3}.$$

The number of tablets used will be based upon the counts within the electronic data capture (eDC). For each bottle, the difference between the tablets dispensed and returned minus any tablets lost will be the tablets used for that bottle. The total number of tablets used will be the sum across bottles. Should a subject not return a bottle, it will be assumed that they returned the average number of tablets that were returned in their other bottles. Subjects with no returned bottles will have missing tablet count and compliance (i.e. no effort will be made to impute values).

The denominator for the compliance calculation includes a + 3 to account for the loading dose received on Study Day 1. This compliance calculation implies a subject who takes treatment for one week but takes all expected tablets for that week will be 100% compliant with treatment.

The eDiary dosing data will be used by study site personnel to monitor dosing in real time but will not be used for dosing and compliance calculations. The days of dosing as measured by the eDiary will be summarized.

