5 STUDY DRUG

5.1 Study Drug Supply, Route of Administration, and Storage

The study drug in this study is serlopitant 5 mg or placebo in a film-coated tablet formulation for oral administration. The serlopitant tablets contain microcrystalline cellulose, mannitol, croscarmellose sodium, silicon dioxide, sodium lauryl sulfate, and magnesium stearate, and are film coated with Opadry® Brown. The placebo tablets contain microcrystalline cellulose, lactose monohydrate, and magnesium stearate, and are film coated with Opadry® Brown.

The study drug will be provided in bottles for storage at room temperature (59–86°F, 15–30°C).

Each bottle provided will include 18 tablets. One bottle will be issued via Interactive Web Response System (IWRS) at each of Baseline, Week 2, and Week 4, and two bottles will be issued via IWRS at Week 6. A total of 5 bottles will be dispensed to subjects completing 10 weeks of study drug treatment.

Additional details regarding study drug supplies can be found in the Pharmacy Manual.

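### The SAP's rule for an unreturned bottle ignores the last dose date, so an adherent subject who stops after Week 2 and keeps the last bottle(s) shows about 102% to 188% compliance instead of 100%

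*SAP*

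**What the plan says.** SAP 2.2 takes compliance from the tablet counts in the case report form. For each bottle, tablets used are those dispensed, less those returned, less any lost. "The total number of tablets used will be the sum across bottles". The denominator is treatment end date minus start date, plus 3: "The denominator for the compliance calculation includes a + 3 to account for the loading dose received on Study Day 1". The SAP states what this should achieve: "a subject who takes treatment for one week but takes all expected tablets for that week will be 100% compliant with treatment".

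When a bottle does not come back, "it will be assumed that they returned the average number of tablets that were returned in their other bottles". There is one exception: "Subjects with no returned bottles will have missing tablet count and compliance". Dosing is also recorded daily in the eDiary, which site staff use to "monitor dosing in real time but will not be used for dosing and compliance calculations". SAP 2.2 and 3.3.5 nevertheless have the eDiary days of dosing summarized and listed separately.

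Protocol 5.1 supplies 18 tablets per bottle, with one bottle at each of Baseline, Week 2 and Week 4; "two bottles will be issued via IWRS at Week 6". Protocol 5.3 gives three tablets on Day 1 and one a day after that. Protocol 8.7 bases compliance on the tablet counts in the eCRF, comparing expected with actual returns.

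**The concern.** The rule treats a subject's bottles as interchangeable, and they are not. The first carries the loading dose, the next two cover 14 days each, and the two Week 6 bottles share 28 days. More importantly, the rule does not look at the last dose date. When a subject stops partway through a bottle and keeps it, the denominator stops growing on that day, but the numerator is still credited with nearly a full bottle.

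This situation is foreseeable. Under Protocol 5.6 an early stopper goes into follow-up and then to the Follow-up visit. Neither the procedures for that visit (Protocol 6.5.11) nor Table 2 in Appendix A includes collection of study drug there.

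What is at stake is the accuracy of two reported quantities, tablets used and compliance. The rule can make an adherent subject look overdosed, and it can hide missed doses.

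**Working it through.** **Inputs.** 18 tablets per bottle (Protocol 5.1); 3 tablets on Day 1, then 1 daily (Protocol 5.3); visits at Days 15, 29 and 43, the target days in SAP Table 3.

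**Assumptions.** The treatment end date is the last dose date. Each new bottle is started on its dispensing day. The Week 6 bottles are used one after the other. No tablets are recorded as lost.

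**The SAP's own figure.** With the last dose on Day D:
- tablets expected = 3 + (D − 1) = D + 2
- denominator = (D − 1) + 3 = D + 2

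One week gives 9/9 = 100% and Day 70 gives 72/72 = 100%. The formula does what the SAP says when all bottles are returned.

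**Expected leftovers for an adherent completer.** Use is 16, 14, 14, 18 and 10, total 72. Returns are therefore 2, 4, 4, 0 and 8.

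**Adherent early stopper who returned the earlier bottles and kept the last one(s) dispensed.** True compliance is 100% in every row.

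| Last dose | Kept | Imputed leftover per kept bottle | Tablets credited | Denominator | Compliance |
|---|---|---|---|---|---|
| Day 15 | bottle 2 | 2 | 16 + 16 = 32 | 17 | 188% |
| Day 20 | bottle 2 | 2 | 32 | 22 | 145% |
| Day 28 | bottle 2 | 2 | 32 | 30 | 107% |
| Day 31 | bottle 3 | (2+4)/2 = 3 | 16 + 14 + 15 = 45 | 33 | 136% |
| Day 42 | bottle 3 | 3 | 45 | 44 | 102% |
| Day 50 | both Week 6 bottles | (2+4+4)/3 = 3.33 | 44 + 2 × 14.67 = 73.33 | 52 | 141% |
| Day 69 | both Week 6 bottles | 3.33 | 73.33 | 71 | 103% |

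Over stop Days 15 to 69 the lowest value is 102% (Day 42) and the highest 188% (Day 15). The result exceeds 110% on 45 of the 55 days (82%). That share describes the rule and does not forecast when subjects will stop.

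**Visit windows.** With Week 2 at Day 12 and a stop on Day 14, bottle 1 has 13 used and 5 left, giving (13 + 13)/16 = 162.5%. With Week 2 at Day 16 and a stop on Day 18, it is (17 + 17)/20 = 170%. On-time visits and a stop on Day 17 give 32/19 = 168%.

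**Only the opened Week 6 bottle kept, stop on Day 50.** Mean leftover is (2+4+4+18)/4 = 7, so 11 tablets are imputed: (44 + 11)/52 = 106%.

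**Adherent completer missing one Week 6 bottle.**
- Emptied bottle missing: mean leftover (2+4+4+8)/4 = 4.5, imputed use 13.5, total 67.5; 67.5/72 = 93.8%.
- Part-used bottle missing: mean leftover (2+4+4+0)/4 = 2.5, imputed use 15.5, total 77.5; 77.5/72 = 107.6%.

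**Missed doses hidden.** A subject misses two doses from bottle 1 and one from bottle 2, stops on Day 20 and keeps bottle 2. Tablets taken are 14 + 5 = 19, so true compliance is 19/22 = 86%. Bottle 1 comes back with 4, so the rule credits 14 + 14 = 28, and 28/22 = 127%.

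**The case against.** The strongest reply is that nothing depends on this number. SAP 2.1 defines no population by compliance, there is no per-protocol set, and no efficacy or safety test uses it. Duration of treatment comes from dose dates. Nor is the error concealed: a reader can set an implausible percentage against the listed eDiary dosing days and the listed study drug data, including lost tablets. All of this stands, and it keeps the point small.

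The reply also limits the size. The excess shrinks as the stop day nears the end of a bottle and when an unopened bottle is returned. A subject who stops before Week 2 and keeps the only bottle has missing compliance, not an inflated value. Tablets recorded as lost are subtracted, which reduces the error. A reader might infer that every early stopper ends far above 100%; the Day 28, 42 and 69 results show otherwise.

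A reader might also infer that the rule inflates an arm's summary or biases the comparison of arms. The documents do not support that. They give no rate of unreturned bottles and do not say that early stoppers are the likeliest to keep one. Protocol 5.9 asks for bottles back at each visit, and the completer case shows that the error can also run downward.

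What the reply does not remove is that a stated rule yields a wrong value for identifiable subjects and breaks the SAP's own 100% property.

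**Conclusion.** The rule is wrong as written, and the consequence is minor. An adherent subject who stops after Week 2 and keeps the last bottle(s) dispensed is reported at about 102% to 188%, depending on the stop day, where the SAP's reasoning requires 100%. An adherent completer missing one Week 6 bottle is reported at 93.8% or 107.6%. The exact figures rest on on-time visits, Week 6 bottles used in sequence, no tablets recorded as lost, and a treatment end date equal to the last dose date. The visit-window check shows that the error does not depend on exact visit timing.

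The effect is confined to the descriptive summaries of tablets used and compliance. Its size at arm level is unknown, and no conclusion on efficacy or safety is in question.

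**What to change.** Delete the rule that borrows the average of the other bottles. Keep the eCRF tablet counts that Protocol 8.7 requires, and compute compliance only over the dosing period covered by returned bottles. The unreturned bottle and its days leave both numerator and denominator. On the examples above:
- Day 20 stop: Days 1 to 14, 16/16 = 100%.
- Day 31 or Day 42 stop: Days 1 to 28, 30/30 = 100%.
- Completer missing a Week 6 bottle: Days 1 to 42, 44/44 = 100%.

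Two details need wording. The two Week 6 bottles should count as one dispensing, because a tablet count cannot show which days each bottle covered. If bottle 1 is the one missing, the loading-dose allowance leaves the denominator with it: 72 − 16 = 56 tablets over Days 15 to 70.

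Report eDiary dosing over the omitted days as a supportive check, with the number of subjects affected per arm. State that tablets used for these subjects refers to returned bottles only. If the sponsor would rather let eDiary dosing replace the missing count, that must first be reconciled with Protocol 8.7 and with the SAP's statement that eDiary data "will not be used for dosing and compliance calculations".

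The cost is a short SAP edit and a small programming change, using data already collected. The downside is that compliance covers a shorter period, and tablets used is understated, for a few subjects.
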